### **4.4. Secondary Endpoints Analysis**

#### **4.4.1. Key Secondary Endpoint**

The endpoint corresponding to secondary study objective subject to type 1 error rate control is specified in Section 1.1 under “Key Secondary (Controlled for Type 1 error) endpoints”.

The null hypotheses corresponding to the key secondary objective can be found in Section 2.

The key secondary objective will be evaluated based on the treatment-regiment and the efficacy estimands (Section 1.1), similar to the primary objective.

#### **4.4.1.1. Mean Changes in Body Weight (kg and lb) from Baseline at 40-week Visit**

The analysis for change in body weight (kg and lb) from baseline (postbaseline to baseline) at Week 40 will be conducted in a manner similar to the primary analysis in Section 4.3.1 (treatment-regimen estimand) and Section 4.3.2 (efficacy estimand) with the following differences:

- For the treatment regimen estimand, the ANCOVA model (Section 4.3.1), baseline category for HbA1c ( $\leq 8.5\%$ ,  $> 8.5\%$ ) will be used as a fixed factor in place of baseline HbA1c as a covariate, and baseline weight will be used as an additional covariate in the statistical model. Imputation of missing values at Week 40 will be done in a similar manner as described in Section 4.3.1. If value of the imputed weight change from baseline is  $<-50$  kg or  $>50$  kg, that value will be set to -50 kg or 50 kg, respectively, to avoid unrealistic imputed values. Similar imputed values (equivalent to kg) will be used for body weight change (lb) from baseline endpoints, to avoid unrealistic imputed values.
- For the efficacy estimand, the MMRM model (Section 4.3.2) will be updated by adding the baseline category for HbA1c ( $\leq 8.5\%$ ,  $> 8.5\%$ ) as a fixed factor in place of baseline HbA1c and baseline weight as an additional covariate. Missing data will be addressed by the MMRM model, and no explicit imputation methods will be used.

#### **4.4.2. Additional Secondary Endpoints**

Additional secondary endpoints except for endpoints specified below will use the efficacy estimand using EAS and will be summarized by treatment and nominal visit.

- change in fasting serum glucose (FSG) (via central lab) from baseline
- HbA1c  $< 5.7\%$ ,  $\leq 6.5\%$ , and  $< 7\%$
- weight loss from baseline of  $\geq 5\%$ ,  $\geq 10\%$ , and  $\geq 15\%$
- change in Waist Circumference from baseline
- change in body mass index (BMI) from baseline
- a composite endpoint “HbA1c  $\leq 6.5\%$  & Weight Loss  $\geq 10\%$  & No-Hypo” defined as
  - HbA1c  $\leq 6.5\%$
  - weight loss  $\geq 10\%$ , and
  - no hypoglycemia, defined as BG  $< 54$  mg/dL ( $< 3.0$  mmol/L) and/or severe hypoglycemia

The endpoints specified above will be analyzed using both treatment regimen and efficacy estimands similar to primary analysis specified in Section 4.3. Unless otherwise specified,

additional secondary endpoints are not subject to type 1 error rate control. Some parameters may be log transformed, if necessary.

#### 4.4.2.1. Analysis for Continuous Outcomes

The analysis to make comparisons between treatment groups for additional secondary continuous outcomes relative to the “efficacy” estimand will be conducted similar to the primary efficacy analysis in Section 4.3.2. The MMRM model will be used for endpoints that have repeated measures over time and the ANCOVA model will be implemented to assess for specific time points. The MMRM model will be updated by adding the baseline category for HbA1c ( $\leq 8.5\%$ ,  $> 8.5\%$ ) as a fixed factor in place of baseline HbA1c, and corresponding baseline values as an additional covariate. Missing data will be addressed by the MMRM model, and no explicit imputation methods will be used. The ANCOVA model (Section 4.3.1) will be updated by adding the baseline category for HbA1c ( $\leq 8.5\%$ ,  $> 8.5\%$ ) as a fixed factor in place of baseline HbA1c, and corresponding baseline values (if available) will be used as an additional covariate in the statistical model.

For the analysis of FSG, waist circumference, and BMI using the treatment regimen estimand, the ANCOVA model (Section 4.3.1) will be implemented with baseline category for HbA1c ( $\leq 8.5\%$ ,  $> 8.5\%$ ) as a fixed factor in place of baseline HbA1c as a covariate and baseline values will be used as an additional covariate in the statistical model.

#### 4.4.2.2. Analysis for Binary Outcomes

The analysis for binary outcomes relative to the “efficacy” estimand will be performed using EAS with missing values imputed by the predicted value from the MMRM model specified in Section 4.3.2, and dichotomized data will then be derived based on continuous imputed values. After dichotomizing, the data is analyzed using a logistic regression model.

In addition, analysis will be conducted utilizing data using EAS from baseline through the 40-week visit with the aid of a longitudinal logistic regression with repeated measurements with treatment, visit, treatment-by-visit interaction, number of background OAMs (0 to 1, 2 to 3), dulaglutide dose at screening, region, baseline category for HbA1c ( $\leq 8.5\%$ ,  $> 8.5\%$ ) as fixed effect, and baseline of the corresponding variable as covariate. In case the longitudinal logistic model does not converge due to small number of events, logistic regression will be utilized at nominal visits.

- For analysis of HbA1c binary endpoints, the logistic model will include treatment, number of background OAMs (0 to 1, 2 to 3), dulaglutide dose at screening, region as fixed effects, and baseline HbA1c as covariates.
- For analysis of weight related binary endpoints, the logistic model will include treatment, number of background OAMs (0 to 1, 2 to 3), dulaglutide dose at screening, region and baseline category for HbA1c ( $\leq 8.5\%$ ,  $> 8.5\%$ ) as fixed effects, and baseline weight as covariates.

- For analysis of composite binary endpoints, the logistic regression model will include treatment, number of background OAMs (0 to 1, 2 to 3), dulaglutide dose at screening and region as fixed effects, and baseline HbA1c, and baseline weight as covariates

The analysis for binary outcomes relative to the “treatment-regimen” estimand will be performed using FAS at baseline and at the 40-week visits with the aid of a logistic regression with multiple imputation of missing data at the 40-week visit (see Section 4.4.1 for details), and dichotomized data will then be derived based on continuous imputed values. After dichotomizing, the data is analyzed using a logistic regression model. Statistical inference over multiple imputations will be guided by Rubin (1987).

- For analysis of HbA1c binary endpoints, the logistic model will include treatment, number of background OAMs (0 to 1, 2 to 3), dulaglutide dose at screening, region as fixed effects, and baseline HbA1c as covariates.
- For the analysis of weight-related binary endpoints, the logistic model will include treatment, number of background OAMs (0 to 1, 2 to 3), dulaglutide dose at screening, region, baseline category for HbA1c ( $\leq 8.5\%$ ,  $> 8.5\%$ ) as fixed effects, and baseline weight as covariates.
- For analysis of composite binary endpoints, the logistic regression model will include treatment, number of background OAMs (0 to 1, 2 to 3), dulaglutide dose at screening and region as fixed effects, and baseline HbA1c and baseline weight as covariates.

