7.2. Participant Discontinuation/Withdrawal from the Study

Discontinuation is expected to be uncommon.

A participant will be discontinued from the study:

- at any time at the participant's own request
- at the request of the participant's designee, for example, legal guardian
- if the participant is diagnosed with T1D or LADA
- if the participant is diagnosed with a malignancy after randomization
 - **Exceptions:**
 - basal or squamous cell skin cancer
 - *in situ* carcinomas of the cervix, and
 - *in situ* or Grade 1 (for example, Gleason 6 or lower) prostate cancer
- at the discretion of the investigator for safety, behavioral, compliance, or administrative reasons
- if a female participant becomes pregnant, see Section 8.3.2, and
- if enrolled in any other clinical study involving an investigational product, or enrolled in any other type of medical research judged not to be scientifically or medically compatible with this study.

At the time of discontinuing from the study, if possible, the participant will complete procedures for an ED visit and posttreatment follow-up, if applicable, as shown in the SoA (Section 1.3).

If the participant has not already discontinued the study intervention, the participant will be permanently discontinued from the study intervention at the time of the decision to discontinue the study.

If the participant withdraws consent for disclosure of future information, the sponsor may retain and continue to use any data collected before such a withdrawal of consent.

If a participant withdraws from the study, the participant may request destruction of any samples taken and not tested, and the investigator must document this in the site study records.

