### 3. Analysis Sets

This table defines the analysis populations and datasets for the purposes of analysis based on the estimands defined in Section 1.1.

Population/Analysis Set	Description
Screened population	All participants who signed informed consent
Randomized population	All participants who are randomly assigned to a treatment arm
Modified intent-to-treat population (mITT)	All randomly assigned participants who are exposed to at least 1 dose of study intervention. Participants will be analyzed according to the treatment they were randomly assigned to regardless of the treatment actually received.
Efficacy Analysis Set (EAS): This analysis set will be used to estimate the efficacy estimand for the primary and key secondary objectives	Data obtained during the treatment period from the mITT population excluding patients who were inadvertently enrolled, excluding data after permanent discontinuation of treatment or initiation of antihyperglycemic rescue medication or prohibited medication
Full Analysis Set (FAS): This analysis set will be used to estimate the treatment-regimen estimand for the primary and key secondary objectives	Data obtained during the treatment period from the mITT population excluding patients who were inadvertently enrolled, regardless of adherence to treatment or initiation of antihyperglycemic rescue medication or prohibited medication (excluding nonstudy tirzepatide or dulaglutide). Data after taking nonstudy tirzepatide or dulaglutide will be excluded.
Safety Analysis Set (SS): This analysis will be used to assess the safety of study treatment	Data obtained during the treatment period plus safety follow-up from the mITT population, regardless of adherence to treatment or initiation of rescue antihyperglycemic medication or prohibited medication.

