#### **4.3.2. Primary Analysis Relative to the Efficacy Estimand**

The primary analysis relative to the “efficacy” estimand will be conducted using HbA1c data in the EAS from baseline through the 40-week visit with the aid of MMRM. Restricted maximum likelihood (REML) will be used to obtain model parameter estimates, and the Kenward-Roger option will be used to estimate denominator degrees of freedom. The response variable of the MMRM model will be change in HbA1c values from baseline obtained at each scheduled postbaseline visit. The independent variables of the MMRM model are treatment, visit, treatment-by-visit interaction, number of background OAMs (0 to 1, 2 to 3), dulaglutide dose at screening, and region as fixed effects, and baseline HbA1c as covariate. Missing data will be addressed by the MMRM model. No explicit imputation methods for missing data will be employed.

An unstructured covariance matrix will be used to model the within-patient errors. If this model fails to converge, the following covariance structures will be tested in the following order:

1. Heterogeneous Toeplitz
2. Heterogeneous First Order Autoregressive
3. Heterogeneous Compound Symmetry
4. Toeplitz
5. First Order Autoregressive
6. Compound Symmetry

The first covariance structure that converges will be used. The resulting least squares mean estimate of mean change from baseline in HbA1c will be summarized by visit and by study treatment.

With the aid of the MMRM analysis, p-values and 2-sided 95% CIs for mean change in HbA1c from baseline to the 40-week visit will be derived and summarized for the tirzepatide 15 mg or MTD arm compared to dulaglutide 4.5 mg or MTD arm

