#### 4.5. Exploratory Endpoints Analysis

Other exploratory (prespecified/nonprespecified in the protocol) endpoints except for endpoints specified below will use the efficacy estimand and will be summarized by treatment and nominal visit. Unless otherwise specified, missing data will not be explicitly imputed, and assessments are not subject to the type 1 error rate control. Some parameters may be log transformed, if necessary.

The endpoint specified below will be analyzed using both treatment regimen and efficacy estimand similar to primary analysis specified in Section 4.3:

- percent change from baseline in body weight.

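### Efficacy-estimand responder analyses fill each missing value with one MMRM prediction before dichotomising, which inflates odds ratios near the arm means and gives 95% intervals that under-cover

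*SAP*

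**What the plan says.** SAP Section 4.4.2.2 sets out the efficacy-estimand analysis of binary outcomes on the EAS: "missing values imputed by the predicted value from the MMRM model specified in Section 4.3.2, and dichotomized data will then be derived". The dichotomised data then go into a logistic regression. Nothing is said about residual or parameter draws, repeated imputation or a variance correction.

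The same section handles the treatment-regimen estimand differently, "with the aid of a logistic regression with multiple imputation of missing data at the 40-week visit", with dichotomising after imputation and inference by Rubin's rules.

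A second efficacy-estimand analysis is listed: "In addition, analysis will be conducted utilizing data using EAS from baseline through the 40-week visit with the aid of a longitudinal logistic regression". It supplements the single-imputation analysis, and the SAP does not say which of the two leads.

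Table 2 sends seven additional secondary endpoints to Section 4.4.2.2: HbA1c <5.7%, ≤6.5% and <7%; weight loss ≥5%, ≥10% and ≥15%; and the composite. Table 4 points the exploratory composite to the same logistic model, but Section 4.5 says "Unless otherwise specified, missing data will not be explicitly imputed", so it is unclear whether the rule reaches that endpoint.

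**The concern.** Dichotomising a predicted mean turns a probability a little above one half into certainty. When the arms differ and the cut-off lies near or between their means, imputed patients fall on opposite sides of it by arm more cleanly than real patients would. The logistic standard error also treats the filled-in values as observed.

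The SAP leaves the predicted value undefined. It could be conditional on the patient's earlier visits, through the covariance in Section 4.3.2 ("An unstructured covariance matrix will be used to model the within-patient errors"), or it could use fixed effects only. A programmer could follow the text and produce either, and the size of the problem depends strongly on which.

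The share of missing values is more than study withdrawal, of which Protocol Section 7.2 says "Discontinuation is expected to be uncommon". The EAS is also defined as "excluding data after permanent discontinuation of treatment or initiation of antihyperglycemic rescue medication or prohibited medication". At stake are responder odds ratios under the estimand that the sponsor intends to use in publications.

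**Working it through.** **Inputs from the documents (SAP Section 5).** 250 randomised 1:1, so 125 per arm; efficacy-estimand difference 0.60 and SD 1.1; 15% discontinuation, used here as the missing share at Week 40.

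**The plan's own figures.** Two-group t-test, noncentrality = difference / (SD × √(2/n)), two-sided 0.05:
- 0.58 / (1.3 × √(2/125)) = 3.53, power 94.0%; with 106 per arm (15% lost), 89.9%.
- 0.60 / (1.1 × √(2/125)) = 4.31, power 99.0%; with 106 per arm, 97.7%.

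The stated powers of at least 90% and 95% reproduce (the 89.9% is 90% to rounding). The documents give no odds ratio or coverage for the responder endpoints.

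**Mechanism, conditional prediction.** If the last observed visit correlates ρ with Week 40, the conditional SD is 1.1 × √(1 − ρ²): 0.40 for ρ = 0.93 and 0.58 for ρ = 0.85. A patient predicted at 6.4% then truly has HbA1c ≤6.5% with probability Φ(0.1/0.40) ≈ 60% or Φ(0.1/0.58) ≈ 57%, but is counted as 100%.

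**Mechanism, fixed-effects prediction, ignoring covariates.** With assumed means 6.9 and 6.3, true rates of ≤6.5% are Φ(−0.4/1.1) = 0.358 and Φ(0.2/1.1) = 0.572, an odds ratio of 2.40. Every missing dulaglutide value is predicted at 6.9 (non-responder) and every missing tirzepatide value at 6.3 (responder). Rates become 0.85 × 0.358 = 0.304 and 0.85 × 0.572 + 0.15 = 0.636, an odds ratio of 4.00. Baseline covariates spread the predictions, so the simulated inflation below is smaller.

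**Simulation.** 2000 trials per scenario (500 for multiple imputation, 20 imputations), 8 post-baseline visits, dropout missing at random with log-odds 0.5 per point of last HbA1c. The MMRM was fitted by maximum likelihood with unstructured covariance; the logistic model had treatment, baseline and three binary factors. The true odds ratio came from 600,000 complete patients. Monte Carlo SE of coverage is about 0.5–0.7 points (0.9 for multiple imputation). Week 40 means, visit correlations and dropout mechanism are assumptions. Results are in the order AR(1) 0.93 / AR(1) 0.85 / exchangeable 0.8 / exchangeable 0.6.

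| | HbA1c ≤6.5% | HbA1c <7% |
|---|---|---|
| True OR | 2.47–2.50 | 2.51–2.53 |
| Full data: OR | 2.53–2.56 | 2.57–2.63 |
| Full data: coverage | 94.9–95.6% | 94.5–95.7% |
| Conditional prediction: OR | 2.67 / 2.82 / 2.59 / 2.70 | 2.79 / 2.95 / 2.67 / 2.81 |
| Conditional prediction: coverage | 93.4 / 90.1 / 94.8 / 92.8% | 92.2 / 89.8 / 93.2 / 90.8% |
| Fixed effects only: OR | 3.47–3.53 | 3.12–3.20 |
| Fixed effects only: coverage | 73.5–75.4% | 83.2–85.9% |
| Multiple imputation: OR | 2.46–2.56 | 2.48–2.59 |
| Multiple imputation: coverage | 95.6–97.6% | 94.8–96.8% |

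For ≤6.5%, the mean model SE against the empirical SD under conditional prediction is 0.274 vs 0.294, 0.276 vs 0.306, 0.273 vs 0.277 and 0.275 vs 0.295. With full data it is 0.272 vs 0.269–0.275.

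**Where the effect is small or changes (conditional prediction):**
- HbA1c <5.7%: rates understated (12.4–13.3% and 27.4–28.7% against true 13.7% and 29.2%), but OR 2.82–2.90 vs 2.77–2.84 with full data and coverage 93.7–96.2%.
- No true difference (both arms 6.6%): OR 1.00–1.01; coverage 91.1–94.4% (≤6.5%) and 90.7–95.0% (<7%), against 93.7–95.5% with full data.
- 5% missing (AR(1) 0.85, exchangeable 0.6): OR 2.59–2.64 vs 2.55 (≤6.5%) and 2.64–2.72 vs 2.58–2.60 (<7%); coverage 93.0–93.5%, against 94.0–94.8% with full data.
- Means 7.2/6.6 or 6.6/6.0 (AR(1) 0.85, exchangeable 0.6): coverage 89.0–93.3% for these two cut-offs.
- Weight (assumed −4% vs −10%, SD 6.5 points; AR(1) 0.97 / 0.92, exchangeable 0.9 / 0.8). Loss ≥5%: OR 4.87 / 5.27 / 4.78 / 4.92 vs 4.69–4.73 with full data, coverage 94.0 / 90.2 / 94.6 / 93.7%. Loss ≥10%: coverage 92.8–95.2%. Loss ≥15%: 96.2–97.5%.

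**Second simulation, other assumed means (7.04 and 6.44), cut-offs 6.5 to 7.0, 15% missing.** Full data gave OR 2.47–2.51 and coverage 94.5–95.7%. Conditional prediction gave OR 2.67–2.69 and coverage 90.9–91.9% with stronger visit correlation, and OR 2.98–3.05 and 82.4–85.2% with weaker. Fixed effects only gave OR 3.15–3.34 and 74.7–81.6%. Multiple imputation gave OR 2.47–2.50 and 95.0–96.4%.

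The composite and the longitudinal logistic model were not simulated, so no figure is claimed for them.

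**The case against.** The best defence is that the practical harm is narrow. On the conditional reading, only HbA1c ≤6.5% and <7% show a consistent effect. For ≤6.5% the largest shift is ln(2.82/2.53) = 0.109, or 0.109/0.272 = 0.40 of a standard error; under exchangeable 0.8, coverage is 94.8%; and at 5% missing the effect is small. The means, correlations and dropout mechanism are assumed, and the gap between the two simulations' lowest conditional coverages (89.8% and 82.4%) shows how much they matter. The other-means check used only the two correlation settings with the lower coverage in the base case. A longitudinal logistic model without this imputation is already planned, the same endpoints get multiple imputation under the treatment-regimen estimand, and none of them is under type I error control.

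These limits stand and bound the size of the problem. They do not remove it. The longitudinal model is an addition, not a replacement, and is not named as the leading result. The treatment-regimen analysis answers a different question. Lack of type I error control does not excuse a biased estimate or an interval labelled 95% that covers less.

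It is also fair that the treatment-regimen imputation, built on retrieved dropouts, is not a ready-made imputation model here, and that the composite's hypoglycaemia component needs its own rule. Only the dichotomise-and-combine steps carry over directly.

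**Conclusion.** The concern holds. The plan prescribes deterministic single imputation before dichotomising for the efficacy-estimand responder endpoints. When the arms truly differ and the cut-off is near or between their means, the odds ratio is inflated and its interval under-covers. With no true difference, the odds ratio is unbiased and only some under-coverage remains.

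At 15% missing and the base-case means, the size on the conditional reading is about 2–15% inflation for HbA1c ≤6.5% and <7%, usually small for weight loss ≥5% and ≥10%, and negligible for the odds ratio at <5.7% and for coverage at ≥15% weight loss. On the fixed-effects reading it is serious. The direction under the stated condition is secure; the size rests on Week 40 means, visit correlations and a dropout mechanism that the documents do not give. Primary and key secondary conclusions are unaffected. This should be corrected, but it does not threaten the trial's main result.

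**What to change.** In SAP Section 4.4.2.2, replace the single prediction for the efficacy estimand with multiple imputation of the missing continuous Week 40 values under missing at random, drawing parameters and residuals from the MMRM conditional distribution. Use the Section 4.3.2 model for HbA1c and the weight version in Section 4.4.1.1 ("For the efficacy estimand, the MMRM model (Section 4.3.2) will be updated by adding the baseline category for HbA1c") for weight. Impute both jointly for the composite, and state a rule for its hypoglycaemia component. Dichotomise within each imputation, fit the stated logistic model and combine by Rubin's rules.

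Name this as the main efficacy-estimand analysis and the longitudinal logistic regression as supportive. State whether the rule applies to the exploratory composite.

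The cost is SAP wording and a modest programming change, with somewhat more work for the composite. For ≤6.5% the mean SE rises from 0.273–0.276 to 0.283–0.289 (0.283/0.273 = 1.04; 0.289/0.276 = 1.05). Odds ratios will be somewhat less favourable, and the intervals may be slightly conservative (coverage up to 97.6% in the base case).

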**Table 2. Additional Secondary Efficacy Analyses Not Controlled for Type I Error**

Objective	Relative to the Efficacy Measure	Analysis Conducted in a Manner Similar to Section	Additional Information
Additional Secondary Analyses			
To assess the clinical effect of tirzepatide compared to dulaglutide at Week 40	Proportion of patients achieving an HbA1c target value of $< 5.7\%$ , from baseline	Logistic model for both treatment regimen and efficacy estimands specified in Section 4.4.2.2	None
	Proportion of patients achieving an HbA1c target value of $\leq 6.5\%$ , from baseline	Logistic model for both treatment regimen and efficacy estimands specified in Section 4.4.2.2	None
	Proportion of patients achieving an HbA1c target value of $< 7\%$ , from baseline	Logistic model for both treatment regimen and efficacy estimands specified in Section 4.4.2.2	None
	Proportion of patients who achieved weight loss of $\geq 5\%$ , from baseline	Logistic model for both treatment regimen and efficacy estimands specified in Section 4.4.2.2	None

Objective	Relative to the Efficacy Measure	Analysis Conducted in a Manner Similar to Section	Additional Information
	Proportion of patients who achieved weight loss of $\geq 10\%$ , from baseline	Logistic model for both treatment regimen and efficacy estimands specified in Section 4.4.2.2	None
	Proportion of patients who achieved weight loss of $\geq 15\%$ , from baseline	Logistic model for both treatment regimen and efficacy estimand specified in Section 4.4.2.2	None
	Proportion of patients who achieved composite endpoint (“HbA1c $\leq 6.5\%$ & Weight Loss $\geq 10\%$ & No-Hypo”), defined as 
 
• HbA1c <math>\leq 6.5\%</math>
 
• weight loss <math>\geq 10\%</math>, and
 
• no hypoglycemia, defined as BG <math>< 54</math> mg/dL (<math>< 3.0</math> mmol/L) and/or severe hypoglycemia
 
	Logistic model for both treatment regimen and efficacy estimand specified in Section 4.4.2.2	None
	Change from baseline in fasting serum glucose	ANCOVA model in Section 4.4.2.1 for treatment regimen estimand and MMRM model in Section 4.4.2.1 for efficacy estimand	Use baseline fasting serum glucose as a covariate. LSM estimates through 40 weeks will be plotted by study treatment.
	Change from baseline in waist circumference	ANCOVA model in Section 4.4.2.1 for treatment regimen estimand and MMRM model in Section 4.4.2.1 for efficacy estimand	Use baseline waist circumference as a covariate.
	Change from baseline in BMI	ANCOVA model in Section 4.4.2.1 for treatment regimen estimand and MMRM model in Section 4.4.2.1 for efficacy estimand	Use baseline BMI as a covariate.
	Change in IWQOL-Lite-CT Physical Functioning domain score from baseline	ANCOVA model in Section 4.4.2.1	Use baseline IWQOL-Lite-CT Physical Functioning domain score as a covariate.

Abbreviations: ANCOVA = analysis of covariance; BG = blood glucose; BMI = body mass index; HbA1c = hemoglobin A1c; IWQOL-Lite-CT = Impact of Weight on Quality of Life-Clinical Trials Version; LSM = least squares mean; MMRM = mixed-effect model of repeated measures; No-Hypo = No Hypoglycemia.

